## **6.4 Cohort 3 (AD Patients)**

### **6.4.1 Baseline Visit (Day 1)**

AD patients will attend the Unit on the morning of Day 1 when the following assessments will be carried out **prior** to randomisation and dosing:

- EASI, BSA and IGA assessments. For inclusion in the study, an EASI score of between 12 and 48, an IGA score of  $\geq 3$  and BSA affected by AD of  $\geq 10\%$  and  $\leq 50\%$  must be recorded.
- Completion of the Ziarco Itch Questionnaire
- Review of concomitant medications
- Review changes in the subject’s medical history since screening
- Brief physical examination
- Duplicate vital signs (supine blood pressure and pulse rate)
- Review of baseline adverse events
- Completion of body map of skin areas affected by AD and identification and recording of skin area to be treated
- Breath alcohol testing
- Obtain blood and urine samples:
  - Safety laboratory tests (haematology, clinical chemistry and urinalysis)
  - Blood sample for pharmacokinetic analysis of ZPL-5212372
  - Blood sample for baseline reference. Serum to be stored frozen at the MAC through to completion of the study for possible use as a baseline reference should additional safety laboratory tests or markers of disease activity be indicated.
  - Urine for pregnancy testing (pre-menopausal women only)

- Urine drug screen

Provided the patient meets all the study entry criteria they will be randomised to treatment. The IWRS will allocate jars of study ointment to be dispensed to the patient and the appropriate study ointment either 1.0% (w/w) ZPL-5212372 or matched placebo. The patient will be shown how to dispense the study ointment and administer the study ointment by the clinical staff. At least 15 minutes after study ointment application study emollient should be applied under clinical staff's supervision.

Patients may then leave the Unit at the discretion of the supervising clinical staff after being provided with enough study medication and study emollient for at least one week.

Patients will be reminded of the study restrictions and also instructed on study medication dosing requirements and concomitant medications use and study emollient use.

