### **8.5.2 Secondary Endpoints**

The proportion of subjects who achieve an EASI-50 response (50% reduction in EASI score from baseline) at Week 2 will be compared between the treatment groups. Group proportions and the difference between these proportions will be calculated along with the corresponding 90% confidence interval. These data will also be analysed using logistic regression, including treatment and baseline. The odds ratio and accompanying 90% confidence interval will be presented.

The proportion of subjects who achieve an EASI-75 response (75% reduction in EASI) and the proportion of subjects who are responders for IGA score (reduction from baseline of at least 2 points) at Week 2, will be analysed using the same analyses described for the EASI-50 response. The changes from baseline in IGA score will also be summarized using categorical shift tables.

The changes from baseline in body surface area, pruritus NRS score for worst itch, NRS score for sleep disturbance and duration of itching at Week 2 will be analysed using the same analyses described for the primary analysis.

The changes from baseline in VRS score will be summarized using categorical shift tables.

The PGIC score will be summarized and analysed using logistic regression, presenting odds ratios and associated 90% confidence intervals for the comparison between treatment groups.

Secondary endpoints will be analysed using the Full Analysis Set.

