#### 3.3. DETERMINATION OF SAMPLE SIZE

The sample sizes for Cohorts 1 and 2 are not based on formal statistical testing. Their sample sizes are considered sufficient to obtain suitable safety, tolerability and PK data prior to starting Cohort 3.

For Cohort 3 the sample size of 30 subjects has been determined on the basis of comparing the mean ZPL-5212372 Week 2 percentage change from baseline in the Eczema Area and Severity Index (EASI) score to that for placebo. With 20 subjects in the ZPL-5212372 group and 10 subjects in the placebo group, there is 80% power of obtaining a statistically significant result, assuming that there is an improvement of at least 30% with ZPL-5212372 compared to placebo and a standard deviation for the percentage changes from baseline between subjects of 30%. This is based on the analyses described and a 1-sided test at the 5% level of significance.

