### 8.2. SECONDARY ENDPOINTS AND ANALYSIS

#### 8.2.1. EASI-50 and EASI-75

The proportion of subjects who achieve an EASI-50 response will be summarised in the FAS with counts and percentages by treatment group at each visit. The number of missing values will also be presented.

An exact logistic regression analysis will be performed at Week 2. The model will include treatment and baseline EASI score. The odds ratio, p-value and associated exact 90% CI will be presented. Subjects with missing responses will be counted as non-responders.

The proportion of subjects who achieve an EASI-75 response will be analysed in the same way as described for the EASI-50.

SAP Version v2.0 Page 29 of 43

Date: 16th March 2017

The cumulative proportion of subjects achieving a  $\ge x\%$  reduction in EASI at Week 2 will be plotted against x, with different lines for each treatment group. Subjects with missing data will be regarded as having the worst change from baseline and labelled as such on the plot. Horizontal reference lines will be drawn that relate to the 0, 25, 50 and 75% reductions in EASI scores.

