### 8.2.3. Investigators Global Assessment (IGA)

IGA will be summarised for the FAS with counts and percentages by treatment at each visit. The number of missing values will also be presented. Shift tables of change from baseline will also be presented with marginal totals.

IGA response will be summarised at each visit with counts and percentages; missing responses will also be tabulated. An exact logistic regression analysis will be performed for Week 2. Baseline IGA, stratification variable (baseline EASI; ≤20 or >20) and treatment will be included in the models as factors; subjects with missing responses will be counted as non-responders. The odds ratio, p-value and associated exact 90% CI will be presented. This analysis will be repeated for IGA success.

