#### 12. CHANGE FROM ANALYSIS PLANNED IN PROTOCOL

The changes from the analyses specified in the protocol are:

- 1. The definition of responders for IGA score in the protocol has been further clarified and made consistent with the sponsor's previous atopic dermatitis study. The definition has changed from reduction from baseline of at least 2 points, to those subjects who achieve a score of 'Clear' or 'Almost clear', or a reduction of ≥ 2 from baseline. An additional definition of IGA success has also be defined as those subjects who achieve a score of 'Clear' or 'Almost clear'.
- 2. The protocol stated that the changes from baseline at Week 2 in NRS sleep disturbance and duration of itch will be analysed using ANCOVA, however it has been decided that it is sufficient to only summarize these endpoints by treatment group and visit. Only the NRS endpoint daily pruritus will be analysed.
- 3. The protocol stated that the Draize score for Cohort 1 would be summarised by treatment group and the change from baseline in Draize score would also be summarised using categorical shift tables. However, the safety review of Cohort 1 showed that there were very few changes in Draize score; it was therefore decided that summaries were not necessary for this endpoint and the data would only be listed.
- 4. The PK analyses described in the protocol have been modified to reflect the very low and sporadic systemic exposure observed during the safety review meetings for Cohorts 1 and 2.

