### 14. INDEX OF TABLES

The following tables are planned to be generated and numbering is indicative only and may be updated for final reporting based on CSR requirements.

Table Number	Title	Cohort	Population
14.1.1.1	Screened Subject Disposition by Cohort	1,2,3	Screened
14.1.1.2	Subject Disposition by Cohort	1,2,3	Randomised
14.1.3.1	Demography by Cohort	1,2,3	FAS
14.1.3.2.1	Cohort 2: Baseline Characteristics	2	FAS
14.1.3.2.2	Cohort 3: Baseline Characteristics	3	FAS
14.1.3.3	Medical History by Cohort	1,2,3	FAS
14.1.4.1	Prior Medications by Cohort	1,2,3	SAF
14.1.4.2	Concomitant Medications by Cohort	1,2,3	SAF
14.1.4.3.1	Prior Emollient Medications by Cohort	2,3	SAF
14.1.4.3.2	Concomitant Emollient Medications by Cohort	2,3	SAF
14.1.5.1	Study Drug Exposure by Cohort	1,2	FAS
14.1.5.2	Cohort 3: Study Drug Exposure	3	FAS
14.2.1.1	Cohort 3: EASI by Visit	3	FAS
14.2.1.2	Cohort 3: EASI by Visit with Multiple Imputation	3	FAS
14.2.1.3	Cohort 3: ANCOVA of Percent Change from	3	FAS
	Baseline in EASI at Week 2: Observed Case		
14.2.1.4	Cohort 3: ANCOVA of Percent Change from	3	PP
	Baseline in EASI at Week 2: Observed Case		
14.2.1.5	Cohort 3: ANCOVA of Percent Change from	3	FAS
	Baseline in EASI at Week 2: Multiple Imputation		
14.2.1.6	Cohort 3: ANCOVA of Percent Change from	3	FAS
	Baseline in EASI at Week 2: LOCF		
14.2.1.7	Cohort 3: ANCOVA of Percent Change from	3	FAS
	Baseline in EASI at Week 2: Worst Case		
	Imputation		
14.2.1.8	Cohort 3: ANCOVA of Percent Change from	3	FAS
	Baseline in EASI Over Time: Observed Case		
14.2.1.9	Cohort 3: ANCOVA of Percent Change from	3	FAS
	Baseline in EASI at Week 2 by Baseline EASI:		
	Observed Case		
14.2.2.1.1	Cohort 3: EASI-50 by Visit	3	FAS
14.2.2.1.2	Cohort 3: Logistic Regression of EASI-50	3	FAS
14.2.2.2.1	Cohort 3: EASI-75 by Visit	3	FAS
14.2.2.2.2	Cohort 3: Logistic Regression of EASI-75	3	FAS
14.2.2.3.1	Cohort 3: EASI Component Erythema by Visit	3	FAS
14.2.2.3.2	Cohort 3: ANCOVA of Percent Change from	3	FAS
	Baseline in EASI Component Erythema Over		
	Time: Observed Case		

SAP Version v2.0 Page 39 of 43

Date: 16th March 2017

		- 1 .	
Table Number	Title	Cohort	Population
14.2.2.4.1	Cohort 3: EASI Component oedema/papulation by Visit	3	FAS
14.2.2.4.2	Cohort 3: ANCOVA of Percent Change from	3	FAS
14.2.2.4.2	Baseline in EASI Component	3	17.5
	oedema/papulation Over Time: Observed Case		
14.2.2.5.1	Cohort 3: EASI Component Excoriation by Visit	3	FAS
14.2.2.5.2	Cohort 3: ANCOVA of Percent Change from	3	FAS

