	Baseline in EASI Component Excoriation Over		
	Time: Observed Case		
14.2.2.6.1	Cohort 3: EASI Component Lichenification by	3	FAS
	Visit		
14.2.2.6.2	Cohort 3: ANCOVA of Percent Change from	3	FAS
	Baseline in EASI Component Lichenification		
	Over Time: Observed Case		
14.2.3.1	Cohort 3: Investigators Global Assessment (IGA)	3	FAS
	and Shift from Baseline by Visit		
14.2.3.2	Cohort 3: Logistic Regression of Investigators	3	FAS
	Global Assessment (IGA) - Responder		
14.2.3.3	Cohort 3: Logistic Regression of Investigators	3	FAS
	Global Assessment (IGA) - Success		
14.2.4.1.1	Cohort 3: NRS for Pruritus by Visit	3	FAS
14.2.4.1.2	Cohort 3: ANCOVA of Change from Baseline in	3	FAS
	NRS for pruritus at Week 2: Observed Case		
14.2.4.1.3	Cohort 3: ANCOVA of Average Change from	3	FAS
	Baseline in NRS for pruritus Over Days 8, 10 and		
14.2.4.2	15: Observed Case	2	FAS
14.2.4.3	Cohort 3: Sleep Disturbance for pruritus by Visit Cohort 3: Total Duration of itch by Visit	3 3	FAS FAS
14.2.5.1	Cohort 3: Verbal Rating Score (VRS) and Shift	3	FAS
14.2.3.1	from Baseline by Visit	3	FAS
14.2.6.1	Cohort 3: Patient Global Impression of Change	3	FAS
14.2.0.1	(PGIC)	3	1713
14.2.6.2	Cohort 3: Logistic Regression of Patient Global	3	FAS
	Impression of Change (PGIC)		. ,
14.2.7.1	Cohort 3: Body Surface Area (BSA) by Visit	3	FAS
14.2.7.2	Cohort 3: ANCOVA of Change from Baseline	3	FAS
	Body Surface Area (BSA) by Visit at Week 2:		
	Observed Case		
14.2.8	Ziarco ointment Questionnaire by Cohort	1,2,3	FAS
14.2.9.1	Cohort 2: ZPL-5212372 Plasma Concentrations	2	PK
14.2.9.2	Cohort 3: ZPL-5212372 Plasma Concentrations	3	PK
14.2.10	Cohort 2: Pharmacokinetic Parameters	2	PK
14.3.1.1.1	Summary of Adverse Events by Cohort	1,2	SAF

SAP Version v2.0 Page 40 of 43

Date: 16th March 2017

Table Number	Title	Cohort	Population
14.3.1.1.2	Cohort 3: Summary of Adverse Events	3	SAF
14.3.1.2.1	Treatment Emergent Adverse Events By SOC and Preferred Term by Cohort	1,2	SAF
14.3.1.2.2	Cohort 3: Treatment Emergent Adverse Events By SOC and Preferred Term	3	SAF
14.3.1.3.1	Treatment Related Treatment Emergent Adverse Events By SOC and Preferred Term by Cohort	1,2	SAF
14.3.1.3.2	Cohort 3: Treatment Related Treatment Emergent Adverse Events By SOC and Preferred Term	3	SAF
14.3.1.4.1	Treatment Emergent Adverse Events By Maximum Severity by Cohort	1,2	SAF
14.3.1.4.2	Cohort 3: Treatment Emergent Adverse Events By Maximum Severity	3	SAF
14.3.4.1.1	Haematology Clinical Laboratory Tests by Cohort	1,2,3	SAF

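### The SAP drops, without declaring it, the protocol's 90% CI for the difference in responder proportions (EASI-50, EASI-75, IGA response); the exact odds ratio that remains can be unbounded or, for EASI-75, not estimable

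*SAP*

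**What the plan says.** **Protocol.** Section 8.5.2, repeated in the synopsis, says of EASI-50 at Week 2: "Group proportions and the difference between these proportions will be calculated along with the corresponding 90% confidence interval". It then adds a logistic regression on treatment and baseline, with odds ratio and 90% CI. EASI-75 and IGA response are to be analysed the same way.

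**SAP, EASI responders.** Section 8.2.1 gives counts and percentages by group and visit. Its comparison is: "An exact logistic regression analysis will be performed at Week 2. The model will include treatment and baseline EASI score". The output is the odds ratio, p-value and exact 90% CI, with missing counted as non-response. EASI-75 follows the same plan.

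**SAP, IGA response.** Section 8.2.3 gives counts and percentages, then an exact logistic regression: "Baseline IGA, stratification variable (baseline EASI; ≤20 or >20) and treatment will be included in the models as factors".

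**Table index.** For these comparisons SAP Section 14 lists only regression tables, such as "Cohort 3: Logistic Regression of EASI-50" and the logistic-regression table ending "Global Assessment (IGA) - Responder". No table shows a difference in proportions.

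**Declared changes.** SAP Section 12 opens with "The changes from the analyses specified in the protocol are" and gives four items: the IGA responder definition, the ANCOVAs of sleep disturbance and itch duration, the Draize summaries, and the PK analyses. The lost difference and its interval are not among them.

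**The concern.** A planned effect-size interval disappears between protocol and SAP for three responder endpoints, and the list meant to record such changes does not mention it. If an interval is wanted at reporting, its method will be chosen with the data in view.

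The cohort is small: "With 20 subjects in the ZPL-5212372 group and 10 subjects in the placebo group". An exact odds ratio is fragile with sparse data. It has no finite upper limit when placebo has no responder. It can also vanish altogether when the model conditions on a nearly continuous covariate. A difference in proportions has a finite interval in every such case. The SAP does not say what is reported when the exact result is unbounded or does not exist.

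**Working it through.** **1. The plan's own figure.** Inputs from SAP 3.3: 20 v 10 patients, difference 30, SD 30, 1-sided 5%. The noncentrality is (30/30)/√(1/20 + 1/10) = 2.58. With 27 df, power is 80.8%, against the stated 80%. The documents give no response rate, power or precision for the responder endpoints, so every rate below is an assumption.

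**2. No placebo responder.** P(0/10) = (1 − p)^10. For p = 5, 10, 15 and 20% this is 0.599, 0.349, 0.197 and 0.107. In each such trial the exact upper limit is infinite, or there is no estimate.

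**3. What an infinite upper limit leaves.** Unadjusted exact results:
- 8/20 v 0/10: median unbiased odds ratio 8.1, 90% CI 1.41 to infinity.
- 6/20 v 0/10: median unbiased odds ratio 5.2, 90% CI 0.88 to infinity.

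An estimate, a lower limit and a p-value therefore remain.

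**4. When nothing is left.** The EASI models condition on the number of responders and on the sum of their baseline EASI scores. Appendix 11 of the protocol allows half scores, so EASI can move in steps of 0.5 × 0.1 × 1 = 0.05. With few responders, only one split between arms may reproduce the observed sum. The exact distribution is then a single point, and there is no odds ratio, limit or p-value.

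Simulation inputs: normal percentage change with SD 30; active mean = placebo mean − 30; response is a change of −50 or below, or −75 or below. The baseline range comes from protocol 6.4.1: "For inclusion in the study, an EASI score of between 12 and 48". Within it, baseline was assumed uniform in steps of 0.1. There were 10,000 trials per scenario.

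| Placebo mean change (assumed) | 0 | −10 | −20 | −30 | −40 |
|---|---|---|---|---|---|
| EASI-75 rate, placebo / active (%) | 0.6 / 6.7 | 1.5 / 12.2 | 3.3 / 20.2 | 6.7 / 30.9 | 12.2 / 43.4 |
| EASI-75: no estimate (% of trials) | 74 | 42 | 13 | 1.5 | 0 |
| EASI-75: infinite upper limit, in addition (%) | 23 | 47 | 60 | 49 | 28 |
| EASI-50 rate, placebo / active (%) | 4.8 / 25.2 | 9.1 / 36.9 | 15.9 / 50.0 | 25.2 / 63.1 | 36.9 / 74.8 |
| EASI-50: no estimate (%) | 4.9 | 0.3 | 0 | 0 | 0 |
| EASI-50: infinite upper limit (%) | 57 | 38 | 19 | 7 | 7 |

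The EASI-75 no-estimate row depends on how finely baseline is recorded: 79/48/16/2/0.1% with 0.05 steps and 51/22/5/0.4/0% with whole numbers. A lognormal baseline (median 20, truncated to 12–48, 0.1 steps) gave about 70/41/11/1% at the first four means.

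The IGA response model was simulated at assumed rates of 15 v 5, 25 v 5, 35 v 10, 45 v 15 and 55 v 25%. It had an infinite upper limit in 59/61/36/21/7% of trials and no estimate in 3/0.4/0/0/0%.

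**5. Does the collapse hide a positive result?** With 0/10 on placebo, the distribution collapses in 97% of cases at 1/20 active, 64% at 2/20, 6% at 3/20, and about 1% or less from 4/20. The unadjusted exact 1-sided p for t/20 v 0/10 is C(20,t)/C(30,t). At t = 3 this is 1140/4060 = 0.28, so no significant result is lost.

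**6. The difference that was dropped (Newcombe 90%).** It is finite for every table:
- 8/20 v 0/10: 40 points (13.5 to 58.1); Miettinen-Nurminen gives 15.6 to 58.4.
- 2/20 v 0/10: 10 points (−12 to 26).
- 0/20 v 0/10: 0 points (−21 to 12).

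**The case against.** The odds ratio is not a late substitute. The protocol planned it beside the difference, and only the exact version is new. Percentages by group are still tabulated, and SAP 8.2.1 adds a cumulative-response plot, so one interval per endpoint is what is lost. The protocol never named a method for that interval. It also commits the study report to describing deviations from planned analyses. All of this stands. It limits the point without answering it, because the interval was planned and Section 12 is where its removal belongs.

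A reader might infer that with 0/10 on placebo the odds ratio tells nothing. It does not follow: a median unbiased estimate, lower limit and p-value normally remain, and for a 1-sided test of benefit the lower limit is the one that matters. Nor does the EASI-75 collapse cost a significant finding. In the worst scenario about 20 × 0.067 + 10 × 0.006 = 1.4 responders are expected among 30 patients, and no method is informative there.

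These are also secondary analyses, without multiplicity control, in a 30-patient cohort. That bears on priority.

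**Conclusion.** The point holds in limited form. The SAP removes the difference in responder proportions and its 90% CI for EASI-50, EASI-75 and IGA response, and does not declare this. What remains can be unbounded above when placebo response is low. For EASI-75 it can be unavailable, almost only when three or fewer patients respond.

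How often this happens depends on placebo response, which the documents do not give. It is frequent at placebo rates of 5–10% and uncommon for EASI-50 once the placebo mean change reaches about −30%. The no-estimate shares also depend on the assumed baseline distribution and recording step.

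The documents do not support a reading that the trial's main conclusion is at risk: the primary ANCOVA keeps its difference and 90% CI. This should be corrected, but it does not undermine the study.

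**What to change.** In SAP 8.2.1, 8.2.3 and the table index, restore the Week 2 difference in responder proportions with a 90% CI, beside the exact odds ratio. Name a method that stays finite with zero cells, for example Newcombe or Miettinen-Nurminen, and count missing as non-response. Keep baseline EASI in the EASI models, as the protocol specifies. State in advance:

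1. The exact 1-sided p-value, where it exists, is the test.
2. If the upper limit is infinite, report the median unbiased odds ratio, the lower limit, the upper limit as infinity, and the p-value.
3. If the exact distribution is a single point, report odds ratio, CI and p-value as not estimable, and show the difference with its CI.

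If the sponsor prefers not to restore the difference, declare and justify its removal in Section 12.

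**Cost.** SAP wording and one line per table; no new data. An unadjusted difference will sit beside a baseline-adjusted odds ratio, and the two can disagree. For 5/20 v 0/10, Newcombe gives 0.4 to 43 points while the unadjusted exact p is 15504/142506 = 0.109, which is why rule 1 is needed. With no true effect, the Newcombe lower limit exceeds zero in up to about 5.8% of trials (exact binomial calculation, at response rates near 85%), slightly above the nominal 5%.

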### 5.4. PER PROTOCOL (PP) ANALYSIS SET

The PP analysis set is only applicable for Cohort 3. It will include all subjects in the FAS who have not violated any inclusion or exclusion criteria and/or deviated from the protocol, in a way that could influence their efficacy assessment. For example subjects will be excluded if they:

- have poor IMP compliance, for example deviated from BID application over the 14 days and/or jar returned without being used. The IMP compliance will be assessed by a clinical review of dosing data and protocol deviations
- receive the incorrect IMP

Subjects will be included in their 'as treated' treatment group. Note that this will be the same as the randomised treatment because receiving the wrong IMP is a major deviation.

Data listings, including protocol deviations (Section 5.6), will be provided to identify subjects to be excluded from the PP analysis set. Precise reasons for excluding subjects will be documented prior to locking the database.

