#### 5.7. PROTOCOL DEVIATIONS

All protocol deviations will be reviewed and documented before database lock. Protocol deviations will be recorded by the site staff, study monitors and medical monitor reviewers. They may also be identified through programmable checks of the data.

Key protocol deviations include:

- Violations of inclusion and exclusion criteria. This includes unknown violations at enrolment and on-study violations, like taking a prohibited medication
- Poor IMP compliance
- Subject receiving the incorrect IMP

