### 6. GENERAL ASPECTS FOR STATISTICAL ANALYSIS

#### 6.1. GENERAL METHODS

All statistical tests for Cohort 3 will be 1-sided at the 0.05 level of significance and accompanied by a 2-sided 90% CI. There will not be any adjustments for multiple comparisons. No statistical testing will be performed with the data from Cohorts 1 and 2.

All summaries and listings will be presented by treatment group and by cohort. For Cohorts 1 and 2, adverse events and pharmacokinetic data will be presented by treatment group and BSA treated (10%, 40% and overall) to assess whether BSA impacts this data.

Only on-treatment records will be summarised for post-baseline visits, except follow-up, unless stated otherwise. A record is considered on-treatment if it is on or before the date of last study medication plus 1 day.

Continuous variables will be summarised using the number of observations (n), mean, standard deviation (SD), 95% Confidence interval (CI) of mean, median, minimum, and maximum. Geometric mean and coefficient of variation (CV) will be included for PK parameters, where appropriate. Categorical variables will be summarised using frequencies and percentages. The number of missing values will be presented in summary tables. The missing count will not include

SAP Version v2.0 Page 22 of 43

Date: 16th March 2017

subjects who have discontinued at earlier visits.

Unless otherwise specified, the estimated mean and median for a set of values should be printed out to 1 more decimal place than the original values, and standard deviations should be printed out to 2 more decimal places than the original values. The minimum and maximum should report the same number of decimal places as the original values. The coefficient of variation will always be reported as a percentage to 1 decimal place. Percentages will be displayed with 1 decimal place; except percentages will not be presented when the count is zero and 100% will be presented as an integer.

Unless stated otherwise, baseline will be defined as the last non-missing measurement prior to administration of the first dose of IMP.

In by-visit summary tables the baseline will be summarised using all available data, but also for each visit using only the baseline data from subjects with available data at the visit; hence the mean change from baseline will equal the mean visit value – mean baseline value.

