### 8. EFFICACY

As Cohort 1 includes healthy volunteers no efficacy data will be collected. Though some efficacy assessments are included for Cohort 2 the data will only be listed and no formal comparisons will be made between the treatment groups. Consequently efficacy will only be assessed for Cohort 3. Hence the following analyses apply to Cohort 3 data.

The observed data summaries for all efficacy endpoints, except PGIC, will only use 'on-treatment' records (i.e. on or before the date of last study medication plus 1 day) for all visits, except baseline and follow-up.

For all ANCOVA analyses the treatment least square means (LS means) and LS mean standard errors, treatment difference estimate, standard error, 1-sided p-value, and 90% CI will be presented. The corresponding SAS ANCOVA output will also be outputted for internal statistical review.

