### 8.2.6. Patient Global Impression of Change (PGIC)

The PGIC scores will be summarised for the FAS with counts and percentages in each treatment group. All data collected will be included.

The PGIC will also be dichotomized into responders, defined as responses of 'Very Much Improved', 'Much Improved' or 'Minimally improved' (1, 2 or 3) and non-responders (4, 5, 6, or 7 plus missing data). The PGIC responder variable will be analysed in the FAS with exact logistic regression. The stratification variable (Baseline EASI; ≤20 or >20) and treatment will be included in the model as factors; the odds ratio, p-value and associated exact 90% CI will be presented.

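### Cohort 3 patients may resume other AD therapy before the Day 15 assessments, and the responder analyses have no rule for a Week 2 value recorded after such therapy

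*SAP*

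**What the plan says.** **Scoring.** The responder endpoints are analysed in the Full Analysis Set (FAS). For EASI-50 and EASI-75, SAP 8.2.1 states: "Subjects with missing responses will be counted as non-responders". For IGA response and success, SAP 8.2.3 states: "subjects with missing responses will be counted as non-responders". For PGIC, SAP 8.2.6 defines "non-responders (4, 5, 6, or 7 plus missing data" as failures. Scores 1 to 3, which include minimal improvement, are responses.

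**Timing.** The last ointment application is on the evening of Day 14 and the Week 2 assessments are at Visit 5 on Day 15 (Protocol 6.4.3), with a window of plus or minus 1 day (Protocol 6). Protocol 3.1 and 5.11 and SAP 3.2 allow Cohort 3 patients to take up other AD treatment, if required, from the end of dosing. Protocol 5.11 also asks that Table 6 medications be withheld, where possible, until follow-up.

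**Controls.**
- Use of prohibited medication is a circumstance for stopping the ointment (Protocol 4.8).
- SAP 6.1 states: "A record is considered on-treatment if it is on or before the date of last study medication plus 1 day". SAP 8 applies the cut with one exception: "The observed data summaries for all efficacy endpoints, except PGIC, will only use" on-treatment records. On the PGIC scores, SAP 8.2.6 adds: "All data collected will be included".
- SAP 5.7 lists "on-study violations, like taking a prohibited medication" among key deviations. SAP 5.4 excludes from the per-protocol (PP) set patients who "deviated from the protocol, in a way that could influence their efficacy assessment".
- The PP analysis repeats the primary analysis only (SAP 8.1.1). Table 14.2.1.4 is the only PP table in the SAP index.

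**The concern.** A topical steroid or calcineurin inhibitor used shortly before the Week 2 assessment could help a patient reach a response threshold. That response would then be credited to the study ointment or to placebo.

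The setting makes this plausible. Patients have moderate to severe disease, stop topical steroids and calcineurin inhibitors for at least a week beforehand, receive no rescue medication and treat themselves at home. Protocol 1.4 itself warns that rescue use could affect the Cohort 3 efficacy data. The permission to resume from the end of dosing nevertheless opens before the endpoint is measured.

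With 20 against 10 patients, a single misclassified patient is visible in the result.

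**Working it through.** **1. The plan's own figure.** Inputs from Protocol 8.9 and SAP 3.3: 20 active, 10 placebo, difference 30, SD 30, one-sided 5%.
- SE = 30 × √(1/20 + 1/10) = 11.62.
- Noncentrality = 30/11.62 = 2.58.
- Noncentral t power is 80.9% with 28 df and 80.8% with 27 df (one covariate).

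The stated 80% is reproduced. No sample-size figure is given for the responder endpoints.

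**2. Which cases the controls miss.**
- *Prohibited use found during dosing.* Ointment stops. An EASI or IGA more than 1 day after the last dose is then off-treatment, so the Week 2 value is probably missing and counted as non-response. This is mostly covered, although SAP 8 words the cut for summaries and not for the models.
- *Use after Day 10, disclosed at Visit 5.* Medications are asked about at visits (Protocol 5.11). Ointment continues, so the Day 15 record is on-treatment. Not covered.
- *On-treatment early termination on Day 13 or 14.* SAP 6.3 assigns it, if possible, to the closest visit. Day 13 is 3 days from Day 10 and 2 from Day 15; Day 14 is 4 and 1. Both go to Day 15. Days 11 and 12 go to Day 10. Not covered, apart from the pre-lock review of outlying visits.
- *Therapy resumed on the evening of Day 14.* The gap before Day 15 is about 12 hours and the record is on-treatment. Not covered. If Visit 5 falls on Day 16 the gap is about 36 hours. With a last dose on Day 14, an EASI or IGA would then fall outside the cut, but PGIC would not.
- *PGIC at any time after such therapy.* PGIC is exempt from the cut on the likely reading. At early termination the patient answers for the last dosing day (Protocol 6.6), which does not remove the effect of a therapy already in use by then.

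**3. Size for one misclassified patient.** The placebo rate moves by 1/10 = 10 points, or the active rate by 1/20 = 5 points. One-sided Fisher examples:

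| Counts, active vs placebo | Difference | p |
|---|---|---|
| 12/20 vs 2/10 | 40 points | 0.045 |
| 12/20 vs 3/10 (one placebo user added) | 30 points | 0.123 |
| 11/20 vs 2/10 | 35 points | 0.074 |
| 12/20 vs 2/10 (one active user added) | 40 points | 0.045 |

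**4. How often one patient changes the verdict.** Assumed true response rates are 20, 30, 40, 50 and 60% on active and 10, 15, 20 and 25% on placebo. Exactly one true non-responder is scored as a responder.
- *Placebo user.* Active count ~ Bin(20, pa), true placebo count ~ Bin(9, pp), observed count = true + 1. Significance is lost in 0.7% (20% vs 25%) to 30% (50% vs 10%) of trials, and in 22% at 50% vs 20%.
- *Active user.* True active count ~ Bin(19, pa), observed count = true + 1, placebo count ~ Bin(10, pp). Significance is gained in 0.6% (20% vs 25%) to 12% (50% vs 15%) of trials, and in 11% at 50% vs 20%.

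The Fisher test stands in for the planned exact logistic regression and ignores its covariates.

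**5. Primary endpoint.** Assume the other therapy improves one patient's EASI change by 30 to 80 points.
- Placebo patient: 30/10 to 80/10 = 3 to 8 points, or 0.26 to 0.69 SE.
- Active patient: 30/20 to 80/20 = 1.5 to 4 points, or 0.13 to 0.34 SE.

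**The case against.** The strongest reply is that the plan already handles most of this. Table 6 drugs must be withheld, use leads to stopping ointment, later EASI and IGA records are off-treatment, and missing counts as failure. Using observed FAS values regardless of deviations is also a legitimate treatment-policy choice, and it matches the primary analysis. These are secondary endpoints in a 30-patient cohort with no multiplicity control. Most of this stands. It is why the point is rated low, and why an added analysis is preferable to replacing the planned one.

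A reader might infer that EASI-50/75 and IGA are widely exposed to prohibited therapy. The documents do not support that: only the routes in step 2 remain. A reader might also take PGIC to be plainly outside the cut. The exemption in SAP 8 is worded for summaries, and the sentence on including all data sits with the score summaries and not with the responder model. Applying both to the model is likely but inferred.

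The verdict-change percentages all assume that one such patient exists, and the documents give no usage rate.

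What the reply does not answer is the permission to resume before Day 15. It is not a deviation that the controls are designed to catch, and the request to withhold where possible covers only Table 6 drugs.

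**Conclusion.** The gap is real but small. Other AD therapy is permitted before the assessment that decides Week 2, and the responder analyses have no rule for a value observed after it, or after prohibited therapy during dosing. The PP analysis does not help here, because it covers only the primary endpoint. The worst-case analysis does not help either, because it covers only the primary endpoint and only missing values.

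One such patient moves a response rate by 10 points (placebo) or 5 points (active). Whether that changes a conclusion depends on assumed response rates and on such a patient existing. Frequency and direction of bias are unknown.

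The documents do not support inferring that the primary result is unsafe. Under the assumed 30 to 80 point effect in one patient, the shift stays below one SE (11.6). Severity: low.

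**What to change.** **1. Timing (Protocol 3.1 and 5.11, SAP 3.2).** State that Cohort 3 patients may resume other AD therapy only after the Day 15 assessments are complete, unless clinically necessary. All three places need the change, or the documents will contradict each other.

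**2. Analysis (SAP 8.2.1, 8.2.3, 8.2.6).** Keep the planned analyses and add a responder analysis that scores certain patients as non-responders. These are patients whom blinded medication review before database lock confirms took a Table 6 therapy for AD after the first dose and before the Week 2 assessment. The therapy must be one able to affect that assessment, for example a topical or systemic steroid, a calcineurin inhibitor or an immunosuppressant. Produce a version of the cumulative EASI plot under the same rule.

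Two limits on the rule:
- Use recorded dates, not those imputed under SAP 7.4. Imputation could turn a steroid stopped in washout, or one resumed after Day 15, into an automatic failure.
- Leave the worst-case analysis in SAP 8.1.1 to missing values. Suppose a patient with baseline EASI 12 and an observed change of -40% were given a worst score of 30 to 40. The change becomes (30-12)/12 = +150% to (40-12)/12 = +233%. That is a move of 190 to 273 points, which shifts the difference by 19 to 27 points (placebo) or 9.5 to 14 (active). This is far more than the 3 to 8 or 1.5 to 4 points being guarded against.

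**Cost.** Resumption is delayed by about 12 hours, or about 36 if Visit 5 falls on Day 16. The protocol change may need amendment approval, and there is slightly more analysis work. No new data are needed: start date and indication are already collected (Protocol 5.11), and deviations and medications are already reviewed before lock (SAP 5.7 and 7.4). Undisclosed use is not reached.
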